7.3.2 Reporting Requirements for this Study

- The SAE Reporting Category, as defined in Version 2.0 of the DAIDS EAE Manual, will be used for this study.
- The study agents for which expedited reporting are required are: Sofosbuvir/Velpatasvir (SOF/VEL) FDC
- In addition to the EAE Reporting Category identified above, other AEs that must be reported in an expedited manner are: all cancers, myopericarditis events, hepatic failures, and autoimmune diseases.

7.3.3 Grading Severity of Events

The Division of AIDS Table for Grading the Severity of Adult and Pediatric Adverse Events (DAIDS AE Grading Table), corrected Version 2.1, July 2017, must be used and is available on the DAIDS RSC Web site at <http://rsc.tech-res.com/clinical-research-sites/safety-reporting/daids-grading-tables>.

7.3.4 Expedited AE Reporting Period

- The expedited AE reporting period for this study is week 0 to week 24/SVR evaluation.

- After the protocol-defined AE reporting period, unless otherwise noted, only suspected, unexpected serious adverse reactions (SUSARs), as defined in Version 2.0 of the EAE Manual, will be reported to DAIDS if the study staff become aware of the events on a passive basis (from publicly available information).

7.4 Study Monitoring

The Protocol Core Team will monitor the conduct and safety of the study via regular summaries of screening, accrual, data delinquency, study and study treatment discontinuation, data and sample completeness with attention to evaluation and time of SVR evaluation, and SAEs.

The DAIDS clinical representative will review and assess EAE reports for potential impact on the study participant safety and protocol conduct as per DAIDS policies, guidance documents, and SOPs as applicable. Additionally, the DAIDS clinical representative will receive aggregated SAE summaries prepared quarterly by the SDAC, as part of the core team monitoring referenced above.

The study will undergo interim review at least annually by an ACTG-appointed Study Monitoring Committee (SMC). The first interim review will occur no more than one year after the enrollment of the first study participant or 6 months after 25% of the study sample (100 participants) have completed 12 weeks on study, whichever occurs earlier. An interim review may also be convened if a concern is identified by the DAIDS clinical representative, the study chairs, or study statistician in consultation with the team. See Section 10 for statistical and other considerations related to interim monitoring.

Detailed plans for study monitoring will be outlined in a Study Monitoring Plan developed by the Statistical and Data Management Center (SDMC) prior to enrollment of the first participant.

Items for SMC interim review include the following: screening and accrual, baseline characteristics of study sample, data (and specimen) completeness, premature study treatment and study discontinuation, unplanned study visits, safety (serious and other adverse events), evaluability for primary efficacy outcome, and for interim reviews including efficacy outcome: SVR outcome estimation.

8.0 CLINICAL MANAGEMENT ISSUES

8.1 Toxicity

Criteria for participant management, dose interruptions, dose adjustments and discontinuation, or changes in treatment will be described only for toxicities attributable to study drugs (SOF/VEL). The grading system for drug toxicities is located in the DAIDS AE Grading Table (see section 7.2).

NOTE: The team must be notified via e-mail within 72 hours regarding toxicities that result in a change in study regimen ([contact]).

It is possible that some participants will experience transient or prolonged AEs during the study. However, it is important to note that, in this trial, there are no scheduled on-treatment visits and hence, participants must call the site and schedule unplanned study visits in order for AEs to be identified. AE-related unplanned study visits will be handled as listed below. However, at week 24, information on any AEs participants may have experienced during the prior 24 weeks, particularly while on study medication, will be collected.

8.2 Management of Side Effects of SOF/VEL

There are no signature abnormalities associated with SOF/VEL. If an SAE occurs, the site investigator has the option to discontinue study treatment. However, prior to the discontinuation of study drugs, the study core team should be contacted by email ([contact]).

Participants who meet any of the following laboratory criteria should stop treatment with SOF/VEL:

- Confirmed elevation of ALT and/or AST >5 x entry values measured while on study treatment measured at unplanned study visits.
- Confirmed direct bilirubin 3 x ULN and >2.0 mg/dL
- Any Grade 3 or greater rash associated with constitutional symptoms assessed as related to treatment with SOF/VEL.
- Any Grade 4 event assessed as related to treatment with SOF/VEL

Dose modification of SOF/VEL will not be allowed in the study. If SOF/VEL is discontinued for toxicity reasons, it should not be restarted.

NOTE: Grades 1 and 2 AEs associated with SOF/VEL require no change in study treatment.

8.3 Pregnancy

Pregnancy will result in immediate discontinuation of the study medication and initiation of counseling regarding the lack of information on safety of SOF/VEL in pregnancy. Participants who become pregnant while on study should contact the site to schedule an unplanned study visit (only up to week 22) and will be followed on study/off-treatment until study completion. A visit following the end of pregnancy will be conducted for evidence of AEs in the participant, and an outcome eCRF will be completed. Male participants whose partners become pregnant will continue treatment as outlined in the SOE.

If a female participant has completed the study or chooses to discontinue from the study before the end of the pregnancy, site staff should request permission to contact her regarding pregnancy outcomes at the end of pregnancy. If the information is obtained, pregnancy outcomes will be submitted on an eCRF at the end of the pregnancy.

Pregnancy and pregnancy outcome will be recorded on the eCRFs. Pregnancies that occur on study should be reported prospectively to The Antiretroviral Pregnancy Registry. More information is available at www.apregistry.com. [contact]; [contact]. (For studies conducted at sites outside the United States: Report to The Antiretroviral Pregnancy Registry - [contact]; [contact] or [contact].)

9.0 CRITERIA FOR DISCONTINUATION

9.1 Permanent and Premature Treatment Discontinuation

- Drug-related toxicity (see section 8.1 Toxicity).
- Requirement for prohibited concomitant medications (see section 5.4).
- Pregnancy in a female participant.
- Breastfeeding.
- Completion of treatment as defined in the protocol.
- Participant request to discontinue for any reason.

NOTE: It is important to determine whether the treatment discontinuation is primarily due to an AE, lack of efficacy, or other reason.

- Clinical reasons believed life threatening by the physician, even if not addressed in the toxicity section of the protocol.

9.2 Premature Study Discontinuation

- Request by the participant to withdraw.
- Request of the primary care provider if s/he thinks the study is no longer in the best interest of the participant.
- Participant judged by the investigator to be at significant risk of failing to comply with the provisions of the protocol so as to cause harm to self or seriously interfere with the validity of the study results.
- At the discretion of the IRB/Ethics Committee, Food and Drug Administration (FDA), NIAID, Office for Human Research Protections (OHRP), other government agencies as part of their duties, investigator, or industry supporter.

10.0 STATISTICAL CONSIDERATIONS

10.1 General Design Issues

This is a single-arm study of 400 participants, to evaluate the feasibility, safety, and efficacy of a MINMON strategy of delivering interferon and RBV-free, pan-genotypic DAA therapy to qualifying persons with active HCV. The outcomes of this study may be used to inform the feasibility and utility of a future randomized controlled trial including a study arm with the MINMON strategy. Because this study includes only one arm, there is no blinding of any study intervention component.

The primary completion date (PCD) for each participant will be timed to be the date when the SVR evaluation takes place. As defined below, SVR evaluation will take place at least 22 weeks following study entry, but may take place any time up to 76 weeks following study entry (i.e., the final study visit evaluation).

Following SVR evaluation, participants will enter Step 2 for post-SVR evaluation follow-up for secondary and exploratory objectives.

10.2 Outcome Measures

10.2.1 Primary Outcome Measures

- 10.2.1.1 Efficacy: Sustained virologic response defined as <LLOQ of HCV RNA in plasma from the earliest sample drawn at least 22 weeks following study entry. Missing results will be treated as SVR non-responders.
- 10.2.1.2 Safety: SAEs as defined by International Council for Harmonization (ICH) guidelines occurring from study entry until 24 weeks following study entry.

10.2.2 Secondary Outcome Measures

- 10.2.2.1 Participant with at least one unplanned clinic visit prior to SVR evaluation
- 10.2.2.2 Reportable AEs (as per section 7.2 of the protocol) not qualifying as SAEs (see primary safety outcome above), occurring from study entry until 24 weeks following study entry.
- 10.2.2.3 Premature discontinuation of study treatment, as defined by self-report by study participants

10.2.3 Other Outcome Measures

- 10.2.3.1 HCV reinfection defined as detectable HCV RNA and HCV sequence from subsequent to evaluation of SVR response, distinct from the baseline sequence and defined only among SVR responders
- 10.2.3.2 Change in FIB-4 between study entry and final study evaluation, defined only among SVR responders
- 10.2.3.3 Treatment emergent RASs among SVR non-responders
- 10.2.3.4 Quality of life (health related utility) before and after HCV cure
- 10.2.3.5 Cost per SVR attained- both globally and stratified by country - calculated using country-specific costs and expressed in US\$ 2017.
- 10.2.3.6 Mode of remote participant contact over time

10.2.3.7 Number and timing of unplanned visits, number of types of evaluations at unplanned visits

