SVR	sustained virologic response (defined as HCV RNA <LLOQ at least 12 weeks after the EOT)
ULN	upper limit of the normal range
VEL	velpatasvir
VL	viral load
WHO	World Health Organization

SCHEMA

A5360

A Single-arm Study to Evaluate the Feasibility and Efficacy of a Minimal Monitoring Strategy to Deliver Pan-genotypic Ribavirin-free HCV Therapy to HCV Infected Populations who are HCV Treatment Naïve with Evidence of Active HCV Infection: The MINMON Study

DESIGN

This is a phase IV open-label, multicenter, prospective study to assess the feasibility and efficacy of a minimal monitoring (MINMON) approach in active hepatitis C virus (HCV)-infected, treatment naïve participants, with and without HIV-1 co-infection, and with no cirrhosis or with compensated cirrhosis only. This study will enroll a cohort of participants with active HCV-infection to follow a minimal monitoring protocol, at US and non-US sites:

- No pre-treatment HCV genotyping;
- Entire treatment course (84 tablets) given to participants at entry;
- No scheduled on-treatment laboratory monitoring or clinic visits;
- Remote contact with participants at week 4 (adherence counseling and locator update) and week 22 (scheduling of SVR visit and locator update).

Participants will receive the fixed-dose combination (FDC) of sofosbuvir/velpatasvir (SOF/VEL) for 12 weeks.

DURATION

72 weeks (see schematic diagram below)

SAMPLE SIZE

400 participants

POPULATION

Men and women aged 18 years or older with active HCV-infection of any genotype, HCV treatment naïve, with or without HIV-1 co-infection. Persons with either compensated cirrhosis or without evidence of cirrhosis are eligible.

[figure not shown]
STRATIFICATION

The study will use stratification factors to limit enrollment by certain subgroups. These stratification factors include geographical location (limited to no more than 132 participants enrolled from sites in the US within the overall study sample), HIV-1 infection (limited to no more than 200 participants being HIV-1 positive within the overall study sample), and cirrhosis status (limited to no more than 80 participants within the overall study sample having compensated cirrhosis). There are no additional restrictions regarding participants who are both HIV-co-infected and have compensated cirrhosis, and or/geographical distribution of those participants.

REGIMEN

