small proportion of patients remain free of HCV at the end of treatment but exhibit HCV viremia at a time point thereafter (SVR or later)—this scenario could be attributable either to relapse or re-infection. HCV sequencing is required to distinguish one from the other. If the sequence of the virus observed is genetically identical to the sequence that was observed at baseline, the person is considered to have relapsed. However, if the sequence observed post SVR is unrelated to the sequence observed at baseline, the individual is considered to have been re-infected. In the pooled ASTRAL studies data which comprised participants from ASTRAL 1, 2, and 3 (n=1035), there were 12 relapses and 1 reinfection [16, 17, 18, 19; see summary here-
<http://www.gilead.com/news/press-releases/2015/9/gilead-announces-svr12-rates-from-four-phase-3-studies-evaluating-a-oncedaily-fixeddose-combination-of-sofosbuvir-sof-and-velpatasvir-vel-qs5816-for-the-treatment-of-all-six-hepatitis-c-genotypes>. In recent data presented from Australia and New Zealand [22, 23], re-infection was observed in 5 out of 54 participants (Incidence of re-infection: 8.88 per 100 p-y) who had undetectable HCV RNA at EOT—active injection drug use was the strongest predictor of re-infection. Data on relapse and re-infection from settings in LMICs such as the study sites included in this study trial are lacking.

Access to and Use of Mobile Phones and Text Messaging Among Non-US Sites

Mobile phones and associated social media and messaging services are widely available in the participating countries. For example, in Brazil, WhatsApp is commonly used to contact participants and remind them of clinic visits. In India, text messaging services are used to remind participants of clinic visits.

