6.3.14 Stored Plasma/PBMCs/Serum

Stored plasma, PBMCs, and serum will be collected at the indicated visits for future HCV/HIV studies and shipped according to the A5360 Laboratory Processing Chart (LPC). Stored specimens will be used after study completion for HCV genotyping/sequencing to assess re-infection versus relapse and estimate SVR by genotype.

Further, the NS5A and NS5B regions of HCV will be sequenced for the earliest sample where HCV RNA is detected post-SVR and the corresponding entry sample will also be sequenced. Sequence data will assist in discriminating between reinfection (entry and post-SVR sequences are not related) versus relapse (entry and post-SVR sequences are identical). Incidence of reinfection will be calculated following the completion of sequencing.

Those who do not achieve SVR (SVR non-responders) will have both baseline and SVR specimens tested for HCV RASs by sequencing the NS5A and NS5B regions.

Any specimens collected during unplanned visits will be stored. See section 6.2.6.

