10.6.3 Secondary Outcomes Analysis

Premature discontinuation of study treatment will be defined from participant self-report either via remote contact prior to SVR evaluation, or at an unplanned visit or by retrospective recall at the week 24 or SVR evaluation visit (whichever occurs first). Those participants missing information from all these mechanisms will be assumed to have prematurely discontinued. The proportion of premature study treatment discontinuation will be estimated and a CI calculated to summarize the range of plausible values using methods parallel to other dichotomous outcomes described above.

Non-serious AEs will be summarized by the Medical Dictionary of Regulatory Affairs (MeDDRA) System Organ Class by the reporting types described in section 7.2.

Those who do not achieve SVR with an observed HCV RNA \geq LLOQ will have both baseline and SVR specimens tested for HCV RASs. Participants in this subset with HCV RASs present in their SVR specimen that were not present in their baseline specimen will be enumerated along with the relative frequencies of new RASs. A description of the observed RASs will also be provided.

Among SVR responders, HCV RNA post SVR follow-up (i.e., Step 2) will be used to evaluate for the HCV reinfection outcome. Detectable HCV RNA, with and HCV sequence distinct from the baseline sequence will qualify for the outcome of HCV reinfection. The absolute number (and relative frequency) of participants meeting this outcome will be summarized along with a 95% CI using methods as described for other dichotomous study outcomes.

Among SVR responders, HCV disease regression will be defined by the absolute change between baseline FIB-4 value and the final study FIB-4 value. The distribution of these absolute changes will also be described using key percentiles.

Further details are outlined in the study's Statistical Analysis Plan (SAP).

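### The protocol's rules for telling reinfection from late relapse disagree, so a participant's own virus with new substitutions can be counted as a reinfection

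*Protocol*

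**What the plan says.** Four places in the protocol bear on how viraemia after an SVR result is classified.

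- **Section 10.2.3.1** (outcome definition, SVR responders only): "HCV reinfection defined as detectable HCV RNA and HCV sequence from subsequent to evaluation of SVR response, distinct from the baseline sequence".
- **Section 10.6.3** (analysis rule): "HCV sequence distinct from the baseline sequence will qualify for the outcome of HCV reinfection". Neither section 10 entry says how different the sequence must be.
- **Section 6.3.14** (sequencing of stored samples): "Sequence data will assist in discriminating between reinfection (entry and post-SVR sequences are not related) versus relapse (entry and post-SVR sequences are identical". The regions sequenced are NS5A and NS5B, in the entry sample and the first viraemic post-SVR sample.
- **Section 2.1** (background): "if the sequence observed post SVR is unrelated to the sequence observed at baseline, the individual is considered to have been re-infected". It reserves relapse for a sequence genetically identical to baseline.

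Two further provisions matter. Section 10.2.3.3 lists "Treatment emergent RASs among SVR non-responders" as an outcome, and section 6.3.14 and SAP section 4.3.2 look for these changes in the same two regions. Section 10.2.1.1 fixes SVR status by the earliest sample at least 22 weeks after entry.

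The primary SAP does not analyse reinfection. Its section 2.1 leaves analyses it does not cover to a Secondary SAP, which is not among the documents supplied.

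**The concern.** Section 10 and section 6.3.14 do not divide the possible results in the same way. The gap falls on a result the protocol itself has reason to expect: the participant's own virus, changed at one or more positions under drug pressure. If that virus is seen at the SVR sample, it is a non-response with a treatment-emergent substitution. If it is first seen at week 48 or 72, section 10 read literally makes it a reinfection.

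What is at stake is objective 1.4.1, the reinfection estimate. Section 3.0 says reinfection rates matter greatly for public health planning. Counting relapses there would overstate new exposure after cure. A second, separate gap is that a late relapse, even if correctly recognised, feeds no named outcome.

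**Working it through.** **1. The rules side by side**

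| Post-SVR sequence against entry sequence | 10.2.3.1 and 10.6.3, read literally | 6.3.14 and 2.1 |
|---|---|---|
| Identical | Not reinfection; no other category | Relapse |
| Related, not identical | Reinfection | No category |
| Unrelated | Reinfection | Reinfection |

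The middle row is the conflict. No passage assigns it consistently.

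**2. Is the middle row realistic?** The regions compared to separate relapse from reinfection, NS5A and NS5B, are the ones searched for treatment-emergent substitutions. A test for relapse that demands identity in regions where change is being sought will fail for some relapses.

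**3. The only related figure in the plan.** The plan states no expected number of reinfections. The nearest figure is the high benchmark in section 10.4: 392 of 400, with a Wilson lower limit above 96%. With p = 0.98, n = 400, z = 1.96:

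- centre = (p + z²/2n) / (1 + z²/n) = 0.98480 / 1.00960 = 0.97543
- half-width = z √(p(1−p)/n + z²/4n²) / (1 + z²/n) = 0.01440
- lower limit = 96.10%, which matches the 96.1% in Table 10.4-3.

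**4. Effect on the reinfection estimate.** Assume 392 SVR responders as the denominator. Each misclassified case adds 1/392 = 0.26 percentage points. With an assumed number of true reinfections (Wilson 95% intervals):

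| True reinfections | Misclassified relapses | Estimate | 95% CI |
|---|---|---|---|
| 5 | 0 | 1.28% | 0.55 to 2.95 |
| 5 | 1 | 1.53% | 0.70 to 3.30 |
| 5 | 2 | 1.79% | 0.87 to 3.64 |
| 10 | 0 | 2.55% | 1.39 to 4.63 |
| 10 | 1 | 2.81% | 1.57 to 4.95 |
| 10 | 2 | 3.06% | 1.76 to 5.27 |

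**5. How many cases are plausible?** Section 2.1 reports no relapse between post-treatment weeks 12 and 24 in three pivotal trials. It gives n = 1,035 for the pooled data and about 98% efficacy, so assume 0.98 × 1,035 ≈ 1,014 responders. For zero events the Wilson upper limit is z²/(n + z²) = 3.84/1,017.84 = 0.38%, or 0.0038 × 392 ≈ 1.5 participants. That evidence covers 12 weeks under close follow-up. Follow-up here runs to week 72, so 1.5 is a guide and not a ceiling. A case must also carry a new substitution to be misclassified.

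**6. Does the reinfection rule touch SVR?** No. Section 10.2.1.1 uses one sample per participant. Viraemia after an SVR result leaves SVR status as it was, whether the later virus is identical, related or unrelated. Rewording 10.2.3.1 moves nobody into or out of the primary count.

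**The case against.** The best defence is that *distinct* in section 10 is shorthand for a different strain. Section 2.1 and section 6.3.14 both say that reinfection requires unrelated sequences, and 6.3.14 says only that sequence data will help to discriminate, which is not a mechanical mismatch rule. A reader might infer from section 10 that the protocol treats any difference from baseline as reinfection. Taken as a whole, it does not say that. This part of the defence stands, and it limits the finding to an inconsistency.

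The defence does not close the gap. The sections that define and count the outcome are 10.2.3.1 and 10.6.3, and they use the looser word. Even if 6.3.14 governs, related but non-identical virus has no category.

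Three further points reduce the weight. Reinfection is an exploratory outcome. The documents' own evidence suggests few late relapses. The Secondary SAP may already hold a relatedness rule, so its absence cannot be asserted; the protocol sections would still need to agree with it. It is also fair to say that the planned sequencing is meant to identify late relapses. What is missing is a place to report them.

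**Conclusion.** The protocol is wrong as written on this point, at low severity. Its rules conflict for a related but non-identical post-SVR sequence, and the literal section 10 rule can overstate reinfection by about 0.26 percentage points per case. That size rests on an assumed 392 responders. The numbers of true reinfections and late relapses used above are also assumptions.

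Two stronger conclusions are tempting and are not supported. One is that the reinfection label hides treatment failures and so flatters the cure rate. The label never enters the SVR estimate; late relapse goes uncounted because SVR is a single-sample outcome, and an identical-sequence relapse would go uncounted too. The other is that one late relapse could reverse the high benchmark, since 391/400 has a Wilson lower limit of 95.78% against 96.10% for 392/400. The arithmetic is right, but the benchmark is defined on SVR and not on cure lasting to week 72, so that move cannot occur in the planned analysis. It could arise only in an added supportive count.

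**What to change.** Align sections 10.2.3.1, 10.6.3 and 6.3.14, and the Secondary SAP, on one rule set before the sequences are read:

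- **Reinfection:** a different genotype or subtype, or a sequence that does not cluster with the participant's own entry sequence, with resistance positions masked.
- **Late relapse:** a sequence related to the entry sequence, whether or not identical.
- **Indeterminate:** anything else, including failed sequencing.

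Report the number of late relapses as a descriptive count beside the unchanged primary SVR result. Optionally add one supportive count that treats them as non-cure, clearly labelled as separate from the benchmark.

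The cost is wording. Entry and first viraemic post-SVR samples are already due to be sequenced in the regions needed. The downside is that a clustering or distance threshold must be chosen in advance, and a few cases may end up indeterminate.
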